**Vapotherm, Inc**  
**Hypercapnia Stabilization RCT NIPPV v HVNI**  
**Confidential**

(systolic BP < 90 mmHg), unremitting tachycardia (>140 or increase by >20% during therapy) or other conditions interpreted by the patient's clinicians as constituting evidence of deterioration.

**Intubation Criteria will be at the discretion of the treating physician.** Researchers will not interfere with clinical management decision. Researchers will attempt to ascertain the physician's rationale for intubation and categorize as one of the following: (may include multiple reasons, or other):

1. Intubation will be undertaken for unremitting respiratory failure despite maximal use of initial and/or crossover therapy as manifested by failure to maintain > 88% despite FIO2 1.0 and optimization of flow and/or PEEP settings.
2. Progressive increase > 10 mmHg in PCO2 and concomitant drop in pH despite maximal attempts to enhance ventilation.
3. Inability to cooperate with therapy in the face of persisting evidence of respiratory failure.
4. Unremitting agitation interfering with ability to cooperate and with persisting evidence of respiratory failure.
5. Deteriorating mental status despite maximal therapy with HVNI and/or NIPPV.
6. Worsening hemodynamic status (systemic SBP <90 mmHg or MAP < 60 mmHg despite fluid resuscitation and use of low dose pressors), unremitting life-threatening arrhythmias, cardiac or respiratory arrest or any other condition which, in the judgment of the clinical care team, warrants intubation.

#### **Phase 3 – Therapy Evaluation Interval #1**

The Therapy Evaluation Interval 1 at 30-minutes will be used to perform a VBG draw for all patients to determine if patients need emergent intubation or if Flow/FiO2 or IPAP/EPAP/FiO2 settings should be adjusted.

At the 30-minutes post-initiation of randomized therapy (HVNI or NIPPV), the patient will be evaluated. Patient Stability Index evaluation will be evaluated by clinicians and recorded at this time. At 30-minutes post initiation of randomized therapy, a venous blood gas sample will be drawn to establish the patient status. Patient status for physiologic parameters (RR, HR, SpO2, BP, RPD) and venous blood gas parameters (PO2, PCO2, pH, bicarbonate, base excess ) will also be collected at this time. For the RPD, the clinician will record patient scores. For VAS, at this time, only patient assessment scores will take place.

Any changes in the assigned therapy settings will be recorded at this interval. Record any relevant treatment intolerance and failure, need for endotracheal intubation, time spent under positive-pressure ventilation , patient mortality, elevation of patient status, and transfer to other inpatient ward/units. Should the patient be placed on intubation prior to this therapy evaluation interval, the physiologic parameters and venous blood gas parameters will be subsequently collected at intubation time. Should the patient be designated by attending clinician for discharge from the ED prior to this therapy evaluation interval, the physiologic parameters, venous blood gas parameters, and final assessment scores (per Phase 6) will be subsequently collected at this time.

#### **Phase 4 – Therapy Evaluation Interval #2**

At the 1-hour post-initiation of randomized therapy (HVNI or NIPPV), the patient will be evaluated. Patient Stability Index evaluation will be evaluated by clinicians and recorded at this time. At 1-hour post initiation of randomized therapy, a venous blood gas sample will be drawn to establish the patient status. Patient status for physiologic parameters (RR, HR, SpO2, BP, RPD) and venous blood gas parameters (PO2, PCO2, pH,

**Vapotherm, Inc**  
**Hypercapnia Stabilization RCT NIPPV v HVNI**  
**Confidential**

bicarbonate, base excess ) will also be collected at this time. For the RPD, the clinician will record patient scores. For VAS, at this time, only patient assessment scores will take place.

Any changes in the assigned therapy settings will be recorded at this interval. Record any relevant treatment intolerance and failure, need for endotracheal intubation, time spent under positive-pressure ventilation, patient mortality, elevation of patient status, and transfer to other inpatient ward/units. Should the patient be placed on intubation prior to this therapy evaluation interval, the physiologic parameters and venous blood gas parameters will be subsequently collected at intubation time. Should the patient be designated by attending clinician for discharge from the ED prior to this therapy evaluation interval, the physiologic parameters, venous blood gas parameters, and final assessment scores (per Phase 6) will be subsequently collected at this time.

#### **Phase 5 – Therapy Evaluation Interval #3**

At the 4-hour post-initiation of randomized therapy (HVNI or NIPPV), the patient will be evaluated. Patient Stability Index evaluation will be evaluated by clinicians and recorded at this time. At 4-hour post initiation of randomized therapy, a venous blood gas sample will be drawn to establish the patient status. Patient status for physiologic parameters (RR, HR, SpO2, BP, RPD) and venous blood gas parameters (PO2, PCO2, pH, bicarbonate, base excess) will also be collected at this time. For the RPD, the clinician will record patient scores. For VAS, at this time, patient assessment scores will take place. Clinician VAS scores may take place either at this Phase, or at Study End (Phase 6).

Any changes in the assigned therapy settings will be recorded at this interval. Record any relevant treatment intolerance and failure, need for endotracheal intubation, time spent under positive-pressure ventilation, patient mortality, elevation of patient status, and transfer to other inpatient ward/units. Should the patient be placed on intubation prior to this therapy evaluation interval, the physiologic parameters and venous blood gas parameters will be subsequently collected at intubation time. Should the patient be designated by attending clinician for discharge from the ED prior to this therapy evaluation interval, the physiologic parameters, venous blood gas parameters, and final assessment scores (per Phase 6) will be subsequently collected at this time.

#### **Phase 6 – Study End & Assessment Scores**

Following the Therapy Evaluation Interval at 4 hours, Phase 6 will be implemented, which concludes with Study End. Patients will be actively screened for adverse events. Any information regarding patient intubation and rationale, if it pertains, will be recorded, if not previously recorded. The therapy settings at time of study end will be recorded. Any patient disposition information during the time course of these study procedures will be recorded, in addition to the patient transfer/discharge information (e.g. home, outpatient, hospital ward, etc.). A patient severity assessment score, BAP-65, will be calculated (or data needed for the calculation will be collected) before the study is completed.

At the end of the study, Phase 6 will include VAS for patient assessment score, and clinician assessment score (if not completed during Phase 5).

**Upon completion of this last Phase**, the study testing procedures will be deemed completed, and any final study data will be completed at this time.

#### **Other Medical Care**

**Vapotherm, Inc**  
**Hypercapnia Stabilization RCT NIPPV v HVNI**  
**Confidential**

All other medical treatment will remain the purview of the attending physician and will be administered per institution standards. This head-to-head randomized control trial, performed as a prospective, unblinded, multicenter, 1:1 randomized trial is designed to evaluate the efficacy of HVNI compared to NIPPV in the stabilization and relief of moderate-to-severe hypercapnic respiratory distress upon presentation. It is assumed that the ancillary interventions will follow common clinical practice guidelines and conventions. All treatments given to the subjects will be noted on their CRFs.

**Vapotherm, Inc**  
**Hypercapnia Stabilization RCT NIPPV v HVNI**  
**Confidential**

## VII. Data Collection

**Table 1. Key study data and collection points for each Phase of the Study.**

	Study Start	Baseline Characterization	Therapy @ 30 minutes	Therapy @ 1hr	Therapy @ 4hr	@ Study End
Patient History & Health Profile	X					X
Treatment: Flow & O2	X	X	X	X	X	X
Patient Stability Index		X	X	X	X	
Physiologic Parameters	X	X	X	X	X	
Blood Gas Parameters		X	X	X	X	
Clinician Perception Scores		X			X	X
Patient Perception Scores		X	X	X	X	X

Patient enrollment data collection will include patient history, health, demographics, and current respiratory therapies. Patient data will also include COVID-19 status. Only Phase 1, study start, will record the patient history and background information. All data collection will be noted with date/time as possible by the clinicians and per the SOC or available medical records. Blood samples (VBG) will be drawn within +15/-15 min of the indicated time from therapy initiation. Vital signs and indices will be recorded within +5/-5 of the indicated time from therapy initiation. Vital signs, including heart rate (HR), respiratory rate (RR) and blood oxygen saturation by pulse oximetry (SpO2), will be reported from the patient monitoring systems in use. If patient is intubated this date and time, blood gases, and physiologic parameters will be recorded in addition to the reason for intubation, as deemed by the clinician(s).

For each phase, the following data will be recorded for comparison:

### Physiologic Parameters

- Rated Perceived Dyspnea (RPD), SpO2, HR, RR, BP

### Blood Gas Parameters

- Venous PCO2, PO2, pH, bicarbonate, base excess Patient Stability Index
  - continuous VAS score on a scale from unable to speak, due to severe respiratory distress, up to speaks in full sentences without severe respiratory distress.

### Primary Endpoint

- Primary Parameter – Change in modified Borg (RPD) over 4-hours

### Secondary Endpoints

- Physiologic parameters –SpO2, HR, RR, BP,
- Secondary Blood Gas parameters – Changes in venous PCO2, venous PO2, venous pH, venous bicarbonate, venous base excess
- Patient Stability Index – continuous VAS score on a scale from unable to speak, due to severe respiratory distress, up to speaks in full sentences without severe respiratory distress.

### Tertiary Endpoints – Patient & Clinician Assessment

# Vapotherm, Inc

## Hypercapnia Stabilization RCT NIPPV v HVNI

Confidential

- Patient Assessment
  - Patient assessment of respiratory response to therapy, ranging from Insufficient to Excellent Response, as continuous VAS.
  - Patient assessment of comfort and tolerance of the therapy, ranging from Insufficient to Excellent, as continuous VAS.
- Clinician Assessment
  - Clinician assessment of patient respiratory response to therapy, ranging from Insufficient to Excellent Response, as continuous VAS.
    - “How satisfied were you with the degree of respiratory support that this patient received since presenting and enrolling in the study?”
  - Clinician assessment of patient comfort and tolerance of therapy, ranging from Insufficient to Excellent as continuous VAS.
    - “How satisfied were you with the degree of comfort and tolerance exhibited by this patient on the received therapy since presenting and enrolling in the study?”
  - Clinician assessment of simplicity of set-up and use, ranging from Complex to Simple, as continuous VAS.
    - “During the study procedures, what degree of challenge did you find in setting up and using/adjusting the device providing therapy for this patient?”

## VIII. Statistical Analysis

The data analysis will be “per protocol,” and per the “intention-to-treat” model. Baseline patient demographics and characteristics will be summarized, compared, and appropriate statistical testing will be performed for the continuous and categorical variables. Primary outcomes will be analyzed for statistical significance to test the null hypothesis. Assuming a non-normal data distribution for this randomized study design, the non-parametric Wilcoxon Signed Rank Sum test will be performed with significance interval of 0.05 on all applicable variables. Parametric analytical analogues (e.g. t-test) will be used if the measurements present a normal distribution. Otherwise, for the categorical variables, the Fisher’s Exact test will be performed and shown by category. Data for patient parameters will be compared across treatment arms and time-period using Repeated Measures analysis ANOVAs to assess dependence on treatment and interactions with time. Data will be compared and graphed accordingly for a visual comparison with accompanied statistical notations. Significance will be accepted where  $p < 0.05$ . Analyses will be performed using SAS version 9.2 or higher or comparable statistical software.

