**Vapotherm, Inc**  
**Hypercapnia Stabilization RCT NIPPV v HVNI**  
**Confidential**

## II. Overall Study Objective

The **overall objective** of this randomized study is to evaluate the efficacy of HVNI, in comparison to NIPPV, to clinically stabilize and provide respiratory therapy to patients who have COPD with moderate-to-severe hypercapnic respiratory distress upon presentation.

The **hypothesis**: HVNI is comparable to NIPPV in the stabilization and relief of moderate-to-severe hypercapnic respiratory distress upon presentation, by relieving the patient's dyspnea (breathlessness) within 4 hours to a comparable degree to NIPPV.

$$H_0: \mu_T \leq \mu_C - 1$$

$$H_a: \mu_T > \mu_C - 1,$$

where  $\mu_T$  and  $\mu_C$  are the improvement in modified BORG at 4 hours for treatment (Vapotherm) and control (NIPPV), respectively, and the non-inferiority margin is 1.

To test this hypothesis, the study will be conducted with the following specific aims:

**Aim #1: Primary Outcome.** The primary endpoint is to evaluate the patient's relief of dyspnea, as measured by the modified Borg, rated perceived dyspnea [RPD 0-10], during the 4-hour post-therapy initiation interval. These measurements will be compiled over the time course of the study – baseline, 30min, 1h, and 4h.

**Aim #2: Secondary Outcomes.** The secondary endpoints evaluate treatment failure (need for intubation), indices of Work of Breathing (patient vitals [HR, RR, SpO2]), patient's clinical stability during hypercapnic respiratory distress, as measured by an index of patient communication capability [Patient Stability Index: 0-10], venous blood gases (pH, PCO2, PO2, bicarbonate, base excess), basic metabolic panel\* (lactate, Na+, K+, Cl, glucose), and patient disposition (length of stay [LOS]). These measurements will be compiled over the time course of the study – baseline\*, 30min, 1h, and 4h. The Patient Stability Index is described in the protocol.

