**Vapotherm, Inc**  
**Hypercapnia Stabilization RCT NIPPV v HVNI**  
**Confidential**

#### **IV. Study Design**

This will be performed as a prospective, unblinded (by definition), multicenter, 1:1 randomized non-inferiority design clinical trial to evaluate the efficacy of HVNI compared to NIPPV (two approved interventions for the management of acute respiratory distress) in the clinical stabilization and relief of moderate-to-severe respiratory distress requiring ventilatory support upon presentation. Patients deemed to fit the criteria for inclusion will perform the study procedures for one of the study arms of the randomized study design. Patient completion of either of the study arms will provide an evaluation of the efficacy of HVNI or NIPPV in stabilization and relief of respiratory acidosis and will record patient ventilatory/WOB indices, treatment failure, disposition, and physiologic parameters during a 4-hour therapy-response window. Additionally, tertiary outcomes will provide an evaluation of patient comfort, and therapeutic response, per the study aims. Patients are expected to complete the study in one session, per the noted parameter sampling intervals (baseline, 30min, 1hr, 4hr). After the patient completes the randomized study arm (HVNI or NIPPV), the clinicians and patients will complete perception score assessments. The clinical management will otherwise remain unchanged, based on individual study site standard of care and practice.

This study will utilize two arms. Patients presenting with acute hypercapnic respiratory failure (per Inclusion criteria, in need of clinical stabilization and relief of moderate-to-severe respiratory distress) who are escalated to treatment with a non-invasive respiratory support modality will be randomized to one of the following:

- Vapotherm high flow nasal cannula therapy (HVNI) administered as defined below (HVNI arm)
- Non-invasive positive pressure ventilation (NIPPV) delivered via single-limb circuit with a full face mask using a pressure support mechanical ventilator system (e.g., Resironics Vision, V60) administered as defined below (NIPPV arm)

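### Section VIII does not turn the margin-1, one-sided 0.025 test of means defined in Sections II and V into one named analysis with a decision rule

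*Combined protocol and SAP*

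**What the plan says.** Section IV describes a "1:1 randomized non-inferiority design clinical trial to evaluate the efficacy of HVNI compared to NIPPV". Section II sets the null hypothesis as mean HVNI improvement no greater than mean NIPPV improvement minus 1, on the modified Borg at 4 hours, and states that "the non-inferiority margin is 1". The sample-size paragraph in Section V repeats the margin of 1.0 and gives a one-sided alpha of 0.025 with power of 80% or more.

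Section VIII is the only analysis section. Its statements that bear on the primary endpoint are:

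- "Primary outcomes will be analyzed for statistical significance to test the null hypothesis". This is its one link to the hypothesis in Section II.
- Non-normal data are assumed, so "the non-parametric Wilcoxon Signed Rank Sum test will be performed with significance interval of 0.05 on all applicable variables".
- The alternative to the rank test is conditional on the data: "Parametric analytical analogues (e.g. t-test) will be used if the measurements present a normal distribution".
- Patient parameters are "compared across treatment arms and time-period using Repeated Measures analysis ANOVAs to assess dependence on treatment and interactions with time".
- "Significance will be accepted where" p < 0.05.
- On the analysis sets: "The data analysis will be “per protocol,” and per the “intention-to-treat” model".

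Section VIII does not restate the margin or the one-sided 0.025, gives no rule comparing an interval with the margin, and does not say which analysis set carries the conclusion.

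**The concern.** In a non-inferiority trial the primary conclusion depends on one comparison: a confidence limit, or a margin-shifted test, against the margin. Sections II and V supply the hypothesis and the error rate. Section VIII should supply the test and the decision rule, and four of its elements leave them open.

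1. **The named test.** The Wilcoxon wording merges the signed-rank test (paired or one-sample) with the rank-sum test (two independent samples). Signed-rank can describe change within patients, but it cannot compare two independent 1:1 arms.
2. **The level.** The 0.05 has no side. It agrees with Section V only if it is two-sided.
3. **The switch.** Whether a rank test or a t-test is used depends on how the outcome data look, and no criterion is given. The hypothesis and the sample size both concern means.
4. **The deciding set.** Intention-to-treat and per-protocol analyses are both named, with no rule for the case where they disagree. This matters because Section IV allows exclusion after randomization, Section VI lists incomplete data among the reasons for leaving the final population, and Section V allows for 20% attrition.

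The trial is unblinded. Choices left open here could be made, or appear to have been made, after results are known.

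**Working it through.** **Inputs.** From Section V: 32 per arm with endpoint data, true difference 0.9, SDs 2.4 and 2.9, margin 1.0, one-sided alpha 0.025. From Section II: the direction, HVNI minus NIPPV improvement, where higher is better. Section V takes the 0.9 as favouring HVNI, since its table shows changes of -4.143 for HVNI and -3.208 for NIPPV.

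**Step 1: reproduce the plan's sample size.** The distance from the margin is 0.9 + 1.0 = 1.9. By the normal approximation, n per arm = (2.4² + 2.9²)(1.960 + 0.842)² / 1.9² = 14.17 × 7.85 / 3.61 = 30.8, so 31 per arm or 62 in all. With the noncentral t distribution, power is 79.0% at 31 per arm and 80.3% at 32, which gives the stated 64. Allowing 20% attrition, 64 / 0.8 = 80. The stated N is therefore that of a margin-shifted two-sample t-test of means at one-sided 0.025.

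**Step 2: success cut-offs under the two sides.** SE = √(2.4²/32 + 2.9²/32) = 0.6654, with 62 degrees of freedom. Success requires observed difference - t × SE > -1.

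| Level applied to the margin test | t | Half-width | Observed difference must exceed | Type I error at true -1 | Power at true 0.9 | Power at true 0 |
|---|---|---|---|---|---|---|
| One-sided 0.025 (Section V) | 1.999 | 1.330 | +0.33 | 2.5% | 80.3% | 31.5% |
| One-sided 0.05 (contrary to Section V) | 1.670 | 1.111 | +0.11 | 5.0% | 88.1% | 43.7% |

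An observed difference of +0.2 shows the effect. Its lower limit is 0.2 - 1.330 = -1.13 in the first row, which fails, and 0.2 - 1.111 = -0.91 in the second, which passes.

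**Step 3: rank test against t-test.** Both were run against the margin at one-sided 0.025 in simulations of 20,000 trials, with normal data and 32 per arm. At a true difference of 0.9 the t-test succeeds in about 80.4% and the rank-sum test in about 78% (77.9% and 78.4% in two separate runs). The two tests disagree in 5.5% of trials. At a true difference of -1 each rejects in about 2.4%, and at least one of them rejects in 2.9%. So the default test falls about two points short of the stated power, and picking the better result would raise type I error only slightly.

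**Step 4: sensitivity to the SDs.** The text gives 2.4 to treatment and 2.9 to control, while the table gives 2.931 to HVNI and 2.431 to NIPPV. With equal arms the swap does not change the SE. The table's unrounded SDs give SE 0.6732, cut-offs of +0.346 and +0.124, and power of 79.4% and 87.4% at 0.9. The conclusions do not change.

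**The case against.** The strongest reply is that the plan should be read as a whole. Section VIII says the primary outcome tests the null hypothesis, and the only null hypothesis is the margin-shifted, one-directional one in Section II. Section V gives the alpha and its side. The 0.05 is a general level for many variables and, read as two-sided, it agrees with Section V. The Wilcoxon name is plausibly a slip, and naming both analysis sets could mean that both must succeed. The rank-or-t choice has a small effect.

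Much of this stands, and it rules out several stronger readings that a reader might infer:

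- **That the plan has no margin or side.** It has both, in Sections II and V.
- **That the plan tests against zero.** The named tests do so in their usual form, but that is convention and the plan does not say it. Requiring a significant zero-difference result in favour of HVNI would also cost power only: at a true difference of -1 it would succeed in about 0.03% of trials.
- **That a non-significant difference would count as non-inferior.** No section says so.
- **That the planned type I error is 5%.** One-sided 0.05 on the primary endpoint contradicts Section V, so the second row of the table shows the cost of a misreading.

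The joint reading still does not say which test is used, what counts as normal, what interval is compared with -1, or which analysis set decides. It also needs the analyst to supply the side of the 0.05.

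**Conclusion.** The point holds in this limited form: the hypothesis, margin and alpha are defined, but the methods in Section VIII do not match them and do not amount to a decision rule. It must be fixed because it concerns the primary conclusion.

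In size, the default rank test has about 78% power against the promised 80% or more. Applying 0.05 one-sided in error would double type I error from 2.5% to 5% and change the verdict in 7.8% of trials at a true benefit of 0.9 (88.08 - 80.26). The open choice between rank test and t-test matters less. The effect of leaving the deciding analysis set open cannot be quantified from the documents.

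The figures assume 32 evaluable patients per arm, the SDs in Section V and, for the rank test, normal data. The sample size is correct on its own inputs for the t-test.

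**What to change.** Replace the primary-analysis sentences in Section VIII with wording such as:

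> The primary analysis is the HVNI minus NIPPV difference in mean modified Borg improvement (baseline minus 4-hour score) from a two-sample model, adjusted for baseline Borg, with a two-sided 95% confidence interval. Non-inferiority is concluded only if the lower limit is above -1.0 (one-sided 0.025) in both the intention-to-treat and the per-protocol sets.

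In addition:

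- Delete the normality-driven switch for the primary endpoint.
- Rename the test Wilcoxon rank-sum, and keep it for the primary endpoint as a fixed sensitivity analysis, either shifted by the margin or as a Hodges-Lehmann interval against -1.0.
- Label the repeated-measures ANOVA as supportive, and state that the 0.05 used elsewhere is two-sided.

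The cost is wording only. N stays at 64 evaluable and 80 enrolled, and baseline Borg is already collected. Baseline adjustment is not needed to test the hypothesis, and it uses one degree of freedom. The one real downside is that requiring both sets makes power no higher than that of the weaker set. There is little slack: at 31 per arm the unadjusted t-test has 79.0%.

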### **Sample Size:**

This trial will randomize subjects 1:1 to Vapotherm:NIPPV. A total sample size of 64 subjects (~32 per arm) randomized with endpoint data, and a one-sided alpha of 0.025 will provide at least 80% power to demonstrate non-inferiority. This sample size assumes a difference of 0.9 between treatment and control with standard deviation of 2.4 and 2.9 for treatment and control, respectively, and a non-inferiority margin of 1.0.

Allowing for up to 20% attrition, approximately 80 subjects (40 per arm) will be enrolled in order to achieve 64 subjects with an endpoint.

From Doshi et al, comparable moderate-to-severe hypercapnic respiratory distress patient data was analyzed, which informed this sample size calculation's assumed difference and standard deviations in treatment (HVNI) and control (NIPPV) for the modified Borg score.

Change in modified Borg over 4 hours	Mean	Standard Deviation
NIPPV arm (Control)	-3.208	2.431
HVNI arm (Treatment)	-4.143	2.931

The minimal clinically important difference (MCID) for modified Borg was informed from literature, as a difference value of 1.0.

**NOTE:** As this is an Emergency Department or inpatient acute care study, and treatment is often immediate due to need for maintaining patient safety, there is an expected patient dropout (i.e. incomplete or unusable subject number) of randomized & enrolled patients into this study. After presenting to the ED or inpatient acute care setting, should the patients be transferred to another area of the hospital, the study procedures will continue until complete.

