**Phase 2 – Baseline Characterization**

The baseline characterization will provide the initial clinical evaluation. Upon enrollment, randomization, and patient background collection, an venous blood gas sample will be drawn to establish the patient baseline at the time just prior to placing the patient on either of the study arm therapies (HVNI or NIPPV). Patient baseline for physiologic parameters (RR, HR, SpO2, BP, RPD) and venous blood gas parameters (PCO2, PO2, pH, bicarbonate, base excess,) will be collected at this time, prior to the initiation of the assigned/randomized therapy. A basic metabolic panel (BUN, CO2, Creatinine, Glucose, Chloride, Potassium, Sodium, Calcium) will also be collected at this time. For the RPD, the clinician will record patient scores. Patient Stability Index evaluation will be evaluated by clinicians and recorded at this time, described as follows: to assess patient clinical stability using a continuous VAS score on a scale from unable to speak, due to severe respiratory distress, up to speaks in full sentences without severe respiratory distress.

At baseline, only patient perception scores will take place. During the noted study phases, the clinician and the patient will complete VAS perception scores (annotated on 100mm line with an "X") for their randomized study arm (HVNI or NIPPV). Patient & Clinician Perception Assessment will be performed by the clinician or therapist performing or participating in the testing procedures. The Perception Assessments will be completed for each of the three endpoints for clinician assessment and the two endpoints for the patient assessment. For the patient perception/satisfaction these include: (1) relief of symptoms, and (2) comfort/tolerance. For the clinician perceptions these include: (1) expected/perceived patient outcomes, (2) patient comfort & tolerance, and (3) ease of use.

The assigned therapy per randomization will be implemented per the initial settings identified below, after which settings will be titrated per standard practice for optimal effect. Patients will be managed by routine care while study data is captured as per the timeline given in Table 1. Note: All decision making for intubation, treatment regimen, discharge, and disposition will be made per standard practice at each center using the judgment of the PI, Sub-I or their designee.

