### XII. Protocol Deviations

Any deviations from the Data Collection plan identified during monitoring or through other means will be documented on case report forms. These include, but are not limited to items such as the following:

- Deviation from the procedural sequencing, per the protocol
- Failure to complete the Baseline characterization
- Failure to complete all sections of the Study Phases
- Failure to capture time and place in trial of any device failure
- Failure to capture/record data included in the protocol
- Subject inability to complete either of the randomized study arms

If the study site demonstrates a pattern of consistent and frequent deviations, the sponsor will undertake appropriate activities (e.g. re-training) to attempt to bring the site into compliance with the protocol. A pattern of repeated serious deviations from the protocol may result in site termination from the study.

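### Optional improvement, not an error: the primary comparison of Borg change leaves baseline Borg unused as a covariate, and adjusting for it may narrow the confidence interval at the same sample size

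*Combined protocol and SAP*

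**What the plan says.** The Primary Endpoint entry in Section VII names the "Change in modified Borg (RPD) over 4-hours". Section II sets the hypothesis on the same scale: the two means are "the improvement in modified BORG at 4 hours for treatment (Vapotherm) and control (NIPPV), respectively", with a non-inferiority margin of 1.

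For the test, Section VIII states that "the non-parametric Wilcoxon Signed Rank Sum test will be performed with significance interval of 0.05 on all applicable variables". It adds that "Parametric analytical analogues (e.g. t-test) will be used if the measurements present a normal distribution". The only model it names is a repeated-measures ANOVA of patient parameters, for treatment and treatment-by-time effects. That model is not named as the non-inferiority test and lists no baseline covariate.

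Baseline dyspnea (RPD, the modified Borg) is among the parameters that, under Phase 2 of Section VI, "will be collected at this time, prior to the initiation of the assigned/randomized therapy".

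The Sample Size paragraph in Section V assumes "a difference of 0.9 between treatment and control with standard deviation of 2.4 and 2.9" for treatment and control, a one-sided alpha of 0.025 and 64 evaluable patients, about 32 per arm. These are SDs of raw change, with no reduction for adjustment.

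**The concern.** A change score removes baseline completely only if the slope of the 4-hour score on the baseline score is 1. At any other slope the change still depends on where the patient started. That dependence adds variance to an unadjusted comparison, and a baseline-adjusted analysis would remove it.

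Two things are at stake. The first is precision. The sample size meets 80% power with almost nothing to spare: the same t calculation gives 79.0% at 31 evaluable patients per arm and 74.6% at 28. The second is chance imbalance. With about 32 per arm, the arms can differ in baseline Borg by luck, and an unadjusted change score carries part of that difference into the treatment estimate. Adjustment corrects for its linear effect.

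The covariate has to be fixed before outcome data are seen, so the place for it is the plan.

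**Working it through.** **Inputs from the documents.** 32 per arm; one-sided alpha 0.025; margin 1.0; assumed advantage for HVNI 0.9; SDs of change 2.4 and 2.9. The text and the table beneath it assign these SDs to opposite arms. That does not alter the pooled value.

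**Inputs assumed.** The correlation rho between baseline and 4-hour Borg, and the ratio k = 4-hour SD / baseline SD. The documents give neither, so the SD of change is held at the plan's value and rho and k are varied.

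**1. The plan's own figure.**
- SD of change = sqrt((2.4² + 2.9²)/2) = 2.66
- SE = 2.66 × sqrt(2/32) = 0.665
- Noncentrality = (1.0 + 0.9)/0.665 = 2.86; power by noncentral t with 62 df = 80.3%
- 95% CI half-width = 1.999 × 0.665 = 1.330
- Enrolment: 64/(1 − 0.20) = 80

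The stated 64 and 80 reproduce. In 8,000 simulated trials per setting with normal data, the default rank test, read as the two-sample rank-sum test, has about 79% power.

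**2. Effect of adjustment.** The residual variance after ANCOVA, as a fraction of the variance of change, is

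k²(1 − rho²) / (1 + k² − 2·rho·k),

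which is (1 + rho)/2 when k = 1. The slope of 4-hour Borg on baseline is rho·k. Power below uses 61 df.

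With k = 1:

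| | unadjusted | rho 0.3 | rho 0.5 | rho 0.7 |
|---|---|---|---|---|
| Variance ratio | 1 | 0.65 | 0.75 | 0.85 |
| Power, true difference 0.9 | 80.3% | 93.6% | 90.1% | 86.2% |
| 95% CI half-width | 1.330 | 1.073 | 1.152 | 1.227 |
| Unadjusted n per arm for the same precision (32/ratio) | 32 | 49 | 43 | 38 |
| Power, true difference 0 | 32% | 45% | 40% | 36% |

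Allowing for estimation of the slope (variance factor 1 + 1/60) gives 93.3, 89.6 and 85.6% at a true difference of 0.9.

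**3. Dependence on the SD ratio.** Power at a true difference of 0.9:

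| k | rho 0.3 | rho 0.5 | rho 0.7 |
|---|---|---|---|
| 0.75 | 98.5% | 97.4% | 96.4% |
| 1.25 | 88.7% | 84.5% | 81.0% |
| 1.5 | 85.3% | 81.6% | 80.3% |
| 2 | 81.9% | 80.2% | not shown |

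Where the slope is exactly 1 (k = 1.25 with rho 0.8, or k = 2 with rho 0.5), power is 80.2%: no gain, and a loss of about 0.1 percentage point.

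**4. Chance imbalance.** A one-SE difference in mean baseline Borg shifts the unadjusted estimate by |1 − rho·k| × baseline SD × sqrt(2/32), where baseline SD = 2.66/sqrt(1 + k² − 2·rho·k). For k = 1 and rho 0.3, 0.5, 0.7 the implied baseline SD is 2.2, 2.7, 3.4 and the shift is 0.39, 0.33, 0.26 Borg points, against a margin of 1.0. At slope 1 the shift is 0.

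**5. Non-normal data and error rate.** In the same simulations with k = 1 and rho 0.3, 0.5, 0.7, power at 0.9 was 93.7, 89.6, 85.8% for ANCOVA; 93.0, 88.7, 84.9% for ANCOVA with HC3 variance; and 91.5, 87.6, 83.8% for rank-based ANCOVA. The rejection rate at a true difference of −1.0 was 2.0 to 2.6% for every method.

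One check used integer scores from 0 to 10 (assumed latent baseline mean 6.5 and SD 2.6; observed rho 0.38). Power was 77.1% for rank-sum, 79.5% for the t-test, 92.8% for ANCOVA, 91.9% with HC3 and 90.2% for rank-based ANCOVA.

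**The case against.** **An unadjusted change score is a legitimate primary analysis.** The hypothesis, the endpoint and the sample size are all set on raw change. This stands, and it is why the point is an improvement and not an error.

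**The size of the gain rests on assumptions.** Equal SDs with rho 0.3, 0.5, 0.7 imply a correlation between baseline and change of −0.59, −0.50, −0.39. If that correlation is only 0.2 or 0.3 in absolute value, power is 81.8% or 83.8%; at 0 there is no gain. The trial enrols patients in moderate-to-severe distress, so a narrow baseline spread that widens with response is plausible. At k = 2 the gain is nearly nil even at modest rho. This also stands: the gain is unknown and may be nil.

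**Some cells fit poorly on a 0-10 scale.** A uniform 0-10 score has an SD of about 2.9. Equal SDs with rho 0.7 need 3.4, and the nil case at k = 1.25 needs 3.55 and 4.4. This affects both the favourable and the unfavourable cells, so it does not remove the case for adjustment.

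**Other gaps in Section VIII come first.** The test name mixes the paired signed-rank test with the two-sample rank-sum test, no confidence interval is specified for the primary comparison, and the text does not say how the margin enters the test. These are separate points and do stand. An adjusted difference with its confidence limit would partly resolve them.

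**Adjustment might lose patients without a baseline score.** Section XII does foresee "Failure to complete the Baseline characterization". Such a patient has no change score under the current plan either, so no one further is lost.

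**Conclusion.** The concern holds as an optional improvement. Section VIII does not condition the primary comparison on baseline Borg, the measurement is already scheduled, and adjustment costs one degree of freedom.

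The documents cannot fix the size of the benefit. With equal SDs and rho from 0.7 down to 0.3, the gain over the t-test is about 6 to 13 percentage points of power, and the interval is 8 to 19% narrower. It shrinks as the 4-hour SD grows relative to the baseline SD, and it vanishes at slope 1. All figures hold the SD of change at 2.66 with 32 per arm.

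Adjustment does not repair the low power at a true difference of zero, which rises only from 32% to between 36% and 45% in the equal-SD cases. The change is worth making, but the validity of the trial does not depend on it.

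**What to change.** In Section VIII, prespecify as the primary analysis an ANCOVA of 4-hour Borg improvement on treatment with baseline Borg as covariate. Report the adjusted difference, HVNI minus NIPPV, with a two-sided 95% CI, and conclude non-inferiority if the lower limit lies above −1.0.

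Because the plan expects non-normal data and unequal SDs, use a robust (HC3) variance and add a rank-based ANCOVA as supporting analysis. Keep the planned unadjusted test as a sensitivity analysis, named as the two-sample rank-sum test if that is what is meant.

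Before settling this, the sponsor could check the baseline/4-hour correlation and both SDs in the prior-trial data that it used for the sample size. That would replace the assumed range with an estimate.

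The cost is a rewrite of the primary-analysis text in Section VIII and one degree of freedom. No new data, visits or patients are needed, and the sample size can stay as it is.
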